3.2.9 Patients who received major surgery within the past 4 weeks

3.2.10 Subjects with any condition that may impair the ability to swallow or absorb oral medications/investigational product including:

- any lesion, whether induced by tumor, radiation or other conditions, which makes it difficult to swallow capsules or pills
- prior surgical procedures affecting absorption including, but not limited to major resection of stomach or small bowel
- active peptic ulcer disease
- malabsorption syndrome

3.2.11 Subjects with any condition that may increase the risk of gastrointestinal bleeding or gastrointestinal perforation, including

- active peptic ulcer disease
- known intraluminal metastatic lesions
- inflammatory bowel disease (e.g., ulcerative colitis, Crohn's disease) or other gastrointestinal conditions which increase the risk of perforation
- history of abdominal fistula, gastrointestinal perforation or intra-abdominal abscess within 28 days prior to beginning study treatment

3.2.12 History of hemoptysis in excess of 2.5 mL (1/2 teaspoon) within 8 weeks prior to first dose of study drug.

3.2.13 Urine protein/creatinine ratio should be screened by urine analysis. If protein is 1+ or higher, 24-hour urine protein should be obtained and the level should be < 1 g for patient enrollment. Patients with < 1+ proteinuria are eligible following initial determination by urinalysis within 1 week prior to enrollment and do not need the urinalysis repeated.

3.2.14 Patients with clinically significant intercurrent illnesses, including but not limited to, life threatening infection, psychiatric illness/social situations that would limit compliance with study requirements will not be eligible to participate.

3.2.15 Pregnant women are excluded from this study because the effects of the study drugs on the developing fetus are unknown. Because there is an unknown but potential risk for adverse events in nursing infants secondary to treatment of the mother with the study drugs, breastfeeding should be discontinued prior to the first dose of study drug and women should refrain from nursing throughout the treatment period and for 14 days following the last dose of study drug.

3.2.16 HIV-positive patients on combination antiretroviral therapy are ineligible because of the potential for PK interactions.

3.2.17 Patients who require use of coumarin-derivative anticoagulants such as warfarin are excluded. Low molecular weight heparin is permitted for prophylactic use, but not therapeutic use.

3.3 Inclusion of Women and Minorities

Both men and women of all races and ethnic groups are eligible for this trial.

3.4 Screening Evaluation

3.4.1 Histologic confirmation: By the Laboratory of Pathology, NIH. A block or stained slides of primary tumor tissue or of known recurrence will be required from each participant to confirm diagnosis.

- 3.4.2** History and physical examination: Complete history and physical examination (including height, weight, vital signs, performance score, EKG) will be conducted within 72 hours week prior to enrollment. Echocardiogram or MUGA scan for assessment of LV ejection fraction will be performed within 4 weeks prior to enrollment.
- 3.4.3** Imaging Studies (Baseline): Every participant should have an evaluation of known sites of disease as part of the baseline evaluation. All patients will be required to undergo a CT scan of the chest/abdomen/pelvis to evaluate sites of disease within 28 days prior to enrollment. MRI or CT scan with contrast of the brain, MRI liver, MRI for other disease sites, or bone scan may be done as clinically indicated.
- 3.4.4** Laboratory Evaluation: Baseline laboratory data are to be obtained within 72 hours prior to enrollment:
- Hematological Profile: CBC with differential.
 - Biochemical Profile: albumin, alkaline phosphatase, total bilirubin, BUN, calcium, creatinine, glucose, phosphorus, total protein, SGOT[AST], SGPT[ALT], magnesium, potassium, and sodium.
 - Coagulation Profile: PT, PTT, INR
 - Serum or urine pregnancy test for female participants of childbearing potential.
 - Urinalysis for urine protein/creatinine ratio or 24-hour urine for proteinuria if patients have 1+ or greater urine protein/creatinine ratio.
 - Serum liver tests (AST, ALT, serum bilirubin) will be performed as part of a risk mitigation plan before initiation of treatment with pazopanib.

4 REGISTRATION PROCEDURES

Authorized staff must register an eligible candidate with NCI Central Registration Office (CRO) within 24 hours of signing consent. A registration Eligibility Checklist from the Web site (<http://home.ccr.cancer.gov/intra/eligibility/welcome.htm>) must be completed and faxed to [REDACTED]. After confirmation of eligibility at Central Registration Office, CRO staff will call pharmacy to advise them of the acceptance of the patient on the protocol prior to the release of any investigational agents. Verification of Registration will be forwarded electronically via e-mail. Please note that it is very important for all registrars to acquire encrypted e-mail from NIH Help Desk, since the verification of registration includes patient's information. A recorder is available during non-working hours.

Off-Study Procedure: Authorized staff must notify the Central Registration Office (CRO) when a patient is taken off-study. An off-study form from the Web site (<http://home.ccr.cancer.gov/intra/eligibility/welcome.htm>) main page must be completed and faxed to [REDACTED].

5 TREATMENT PLAN

This is an open-label Phase I trial evaluating the combination of pazopanib, an oral VEGFR inhibitor, and ARQ 197, an oral MET inhibitor, in patients with refractory advanced solid tumors. Reported adverse events and potential risks for pazopanib and ARQ 197 are described in [Section 7](#). Appropriate dose modifications for pazopanib and ARQ 197 are described in [Section 6](#). No investigational or commercial agents or therapies other than pazopanib and ARQ 197 may be administered with the intent to treat the patient's malignancy.

The study will be carried out in 2 phases, as described in [Section 5.1](#). The drugs will be administered in 28-day cycles (\pm 1 day for scheduling). Pazopanib tablets should be administered orally without food (at least 1 hour before or 2 hours after eating) once a day. ARQ 197 tablets should be administered orally with food twice daily approximately every 12 hours. A missed or vomited dose should not be replaced. The patient should be instructed to take the next scheduled dose at the regularly scheduled time. Patients will be asked to maintain a Study Medication Diary ([Appendix E](#)) and record each dose of medication. Patients will be given instructions for completing the medication diary and will be asked to return it to the clinic staff at the end of each cycle.

With Amendment H, dated 09/26/2013: For patients who have been on study for six or more cycles and are tolerating treatment well, two months worth of drug may be dispensed at a time; labs and blood pressure monitoring will only be performed once every 2 cycles (every 2 months). More frequent labs and assessment can be performed as clinically indicated.

History and physical examination can be done up to 3 days before start of a new cycle. Patients will be examined on D1, D8 (only for patients who will have tumor biopsy), and D15 in the dose escalation phase, or D1 and D8 in the expansion phase, at the clinical center for the first cycle and prior to every new cycle. Blood pressure (BP) will be checked every 2 weeks during the first 2 cycles in the dose escalation phase and on D1 and D8 of cycle 1 in the expansion phase, and then at the beginning of subsequent cycles. Mid-cycle blood pressure monitoring can be performed by any healthcare provider.

Labs (CBC with differential; serum chemistries, including glucose) will be performed as follows:

- *Dose escalation phase*: every week for the first cycle, then every 2 weeks for cycle 2 and then at the start of each cycle (up to 3 days before start of a new cycle) for the remainder of the study.
- *Expansion phase*: D1 and D8 of cycle 1, then at the start of each cycle (up to 3 days before start of a new cycle).

EKG will be performed as follows:

- *Dose escalation phase*: at baseline, on C1D1 (3-6 hours after the first dose of ARQ 197) and on C1D15 (3-6 hours after the morning dose of ARQ 197) and as clinically indicated.
- *Expansion phase*: at baseline, on C1D1 (3-6 hours after pazopanib), on C1D8 (3-6 hours after pazopanib), on C2D1 (3-6 hours after the morning dose of ARQ 197), and as clinically indicated.

Evaluation of urine protein/creatinine ratio will be performed as follows:

- *Dose escalation phase*: at baseline, on C1D15, then at the start of each cycle.

– *Expansion phase*: at baseline, on C1D8, then at the start of each cycle, and as clinically indicated.

Echocardiogram or MUGA scan for assessment of LV ejection fraction will be performed at baseline and as clinically indicated.

CT scans will be performed at baseline, and repeat imaging scans will be performed every 2 cycles.

As part of a risk mitigation plan for possible hepatic failure, serum liver tests (AST, ALT, serum bilirubin) will be monitored before initiation of treatment with pazopanib and at weeks 3, 5, 7, and 9. Thereafter, monitoring will occur at months 3 and 4, and as clinically indicated. Periodic monitoring will continue after month 4.

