5.3.3 Neutropenia

To reduce the risk of severe myelosuppression events, a complete blood count (CBC) should be performed weekly during cycle 1, every 2 weeks during cycle 2, and at the start of each subsequent cycle (up to 3 days before start of new cycle) in the dose escalation phase. In the expansion phase, CBC will be performed on D1 and D8 of cycle 1, then at the start of each cycle (up to 3 days before start of new cycle). Febrile neutropenia is a life-threatening complication requiring hospitalization and urgent broad-spectrum antibiotics, as well as an aggressive search for the source and microbial cause of the episode. Growth factors to prevent neutropenia will not be administered prophylactically. If necessary, they may be administered according to accepted American Society of Clinical Oncology (ASCO) guidelines to allow re-treatment.

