10 STUDY CALENDAR

Baseline history and physical exam are to be conducted within 72 hours prior to start of protocol therapy; laboratory evaluations (including serum liver tests) and EKG must also be done within 72 hours. Scans, x-rays, and echocardiogram or MUGA scan must be done ≤ 4 weeks prior to the start of therapy. In the event that the patient's condition is deteriorating, laboratory evaluations should be repeated within 48 hours prior to initiation of the next cycle of therapy. The duration of a cycle will be 28 days (± 1 day for scheduling). Start of next cycle may be delayed for up to 1 week to accommodate scheduling conflicts. History and physical examination and laboratory evaluations can be performed up to 3 days before the start of the next cycle.

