10.2 Expansion Phase

	Pre-Study	C1 W1 (D1-7)	C1 W2 (D8-14)	C1 W3 (D15-21)	C1 W4 (D22-28)	C2 W1 (D1-7)	C2 W2 (D8-14)	C2 W3 (D15-21)	C2 W4 (D22-28)	C3 W1 on	Off Treatment
Pazopanib^a		X	X	X	X	X	X	X	X	X	
ARQ 197^a		X	X	X	X	X	X	X	X	X	
Informed consent	X										
Demographics	X										
Medical history	X										
Concurrent meds	X	X-----X									
Physical exam ^b	X		X			X				X	X
Vital signs ^c	X		X			X				X	X
Height	X										
Weight	X					X				X	X
Performance status	X					X				X	X
CBC w/diff, plts ^d	X			X		X				X	X
Serum chemistry ^d	X		X	X		X		X*		X	X
Coagulation	X										
Urine protein/creatinine ratio or 24-hour urine protein ^e	X		X			X				X	X
EKG ^f	X		X			X*					
Echocardiogram/MUGA	X										
Adverse event evaluation		X-----X									X
Tumor measurements	X	Tumor measurements are repeated every 2 cycles. Documentation (radiologic) must be provided for patients removed from study for progressive disease.									X
B-HCG ^g	X										
Tumor biopsies ^h	X		X								
PD blood sampling ⁱ	X	X	X			X					
PG blood sampling ^j	X										
PK blood sampling ^k	X	X									

a: Pazopanib once daily (empty stomach) and ARQ 197 twice daily (with meals) at MTD dose. Single-agent pazopanib from C1D1 to D7 then the combination of ARQ 197 and pazopanib from C1D8 in Cohort A
 
b: Physical examination at Clinical Center should be performed on D1 and D8 and then at the start of each cycle (up to 3 days before start of new cycle). For patients who have been on study for 6 or more cycles and are tolerating treatment well, physical exams may be performed once every 2 cycles (every 2 months).
 
c: BP monitoring by a health care provider should be performed on D1 and D8 of cycle 1 and then at the beginning of subsequent cycles. For patients who have been on study for 6 or more cycles and are tolerating treatment well, BP monitoring may be performed once every 2 cycles (every 2 months). Patients should measure and record their blood pressure at home at least once per day for the duration of the study.
 
d: Serum chemistry (albumin, alkaline phosphatase, total bilirubin, BUN, calcium, creatinine, glucose, phosphorus, magnesium, potassium, total protein, SGOT [AST], SGPT [ALT], sodium) and CBC w/diff, platelets should be performed within 72 hours of enrollment (pre-study) and again on D18 of cycle 1, and
											

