at the start of each cycle (\pm 1 day for scheduling conflicts). For patients who have been on study for 6 or more cycles and are tolerating treatment well, lab tests may be performed once every 2 cycles (every 2 months). Serum liver tests (AST, ALT, serum bilirubin) will also be performed during weeks 3, 5, 7 (*can be collected by patients' local physician), and 9; thereafter, monitoring will occur at months 3 and 4, and as clinically indicated. Periodic monitoring will continue after month 4.

- e: Evaluation of urine protein/creatinine ratio should occur at baseline, on C1D8, then at the start of each cycle (\pm 1 day for scheduling conflicts), and as clinically indicated. If patient has urine protein/creatinine ratio $>1+$, obtain a 24 hour urine for protein and creatinine clearance.
- f: EKG will be performed at baseline, on C1D1 (3-6 hours after the morning dose of pazopanib), on C1D8 (3-6 hours after pazopanib), on *C2D1 (3-6 hours after the morning dose of ARQ 197), and as clinically indicated.
- g: Serum or urine pregnancy test (women of childbearing potential) within 1 week prior to enrollment.
- h: Tumor biopsies are mandatory in the expansion phase: at baseline and on C1D8, 8-12 hours after pazopanib before the first dose of ARQ 197.
- i: Samples will be obtained at the following time points: at baseline, on C1D1 (2, 4, and 6 hours after pazopanib), on C1D8 (pre-drugs), and on C2D1 (pre-drugs).
- j: A sample for the PG study will be obtained at baseline.
- k: Blood samples for PK will be collected from all patients during cycle 1 only on D1 and D7 as specified in [Section 9.2.1.2](#).

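### Expansion-phase cycle 1 blood counts: Sections 5 and 5.3.3 say D1 and D8, while the Section 10.2 calendar says week 3 (D18), probably by a slip, and so drops the count before ARQ 197 starts

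*Combined protocol and SAP*

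**What the plan says.** - **Section 5 (labs, expansion phase):** CBC and chemistry on "D1 and D8 of cycle 1, then at the start of each cycle (up to 3 days before start of a new cycle").
- **Section 5.3.3:** "In the expansion phase, CBC will be performed on D1 and D8 of cycle 1", then at each cycle start, again up to 3 days early.
- **Section 10.2, CBC row:** marked pre-study, in cycle 1 week 3 (D15-21), in week 1 of cycle 2, from cycle 3 on, and off treatment. Cycle 1 weeks 1, 2 and 4 are blank.
- **Section 10.2, footnote d (CBC and chemistry together):** "should be performed within 72 hours of enrollment (pre-study) and again on D18 of cycle 1", then at each cycle start within a day either way.
- **Section 10.2, chemistry row:** the same footnote, but marked in cycle 1 weeks 2 and 3 and in cycle 2 week 3.
- **Section 10.2, footnote d (liver tests):** "Serum liver tests (AST, ALT, serum bilirubin) will also be performed during weeks 3, 5, 7", and week 9.

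In Cohort A pazopanib is given alone on D1 to D7. ARQ 197 is added on D8, after the biopsy (Section 5.1.2).

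**The concern.** Two current instructions name different days for the same safety test, and nothing in the protocol says which one governs. The difference falls around D8, the day the second drug is added.

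The schedule decides when a routine count can trigger the dosing rules. Sections 6.1.3 and 6.1.4 hold both drugs for Grade 3 neutropenia or thrombocytopenia, for Grade 4 thrombocytopenia, and for Grade 4 neutropenia lasting at least 3 days. Section 6 also requires most hematologic toxicity to be at Grade 2 or lower before the next dose of either drug. Decreased neutrophils are listed for both agents in Section 7.1. A laboratory grade that causes no symptoms is seen only if someone draws a count.

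**Working it through.** No sample size, power or error rate is involved, and the plan gives no figure to reproduce. The check compares the statements and counts days.

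**1. Inputs.** C1D1 is day 1 and the cycle is 28 days, so C2D1 is D29. The first ARQ 197 dose is on D8. Cycle-start labs may be up to 3 days early (Sections 5, 5.3.3 and 10), or within 1 day either way (10.2 footnote d). The next cycle may start up to a week late (Section 10), so C2D1 is D36, or D37 if the 1-day cycle window is added. Baseline labs are drawn 0 to 3 days before D1 (72 hours, Section 10).

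**2. Which version was probably meant.** Footnotes b, c, e, f, h and i of 10.2 all use D8; footnote b, for example, reads "Physical examination at Clinical Center should be performed on D1 and D8 and then at the start of each cycle". No D18 visit appears elsewhere. The chemistry row fits the text: week 2 is the D8 draw, and the marks in cycle 1 week 3 and cycle 2 week 3 are the week 3 and week 7 liver tests. So D18 looks like a slip for D8. Correcting that one word is not enough, because the CBC row would still show week 2 blank and week 3 marked, and the liver tests do not include a CBC.

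**3. Gaps under each version and under one combined schedule (days).**

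| Schedule | Before or up to the first on-treatment interval | To the cycle 2 labs, nominal | To the cycle 2 labs, cycle 2 a week late |
|---|---|---|---|
| Text: D8, then labs up to 3 days early | D1 to D8: 7 | 26 - 8 = 18 to 29 - 8 = 21 | 33 - 8 = 25 to 36 - 8 = 28; latest 37 - 8 = 29 |
| Calendar: D18, then labs within 1 day | baseline to D18: 18 - 1 = 17 to 17 + 3 = 20 | 28 - 18 = 10 to 30 - 18 = 12 | 35 - 18 = 17 to 37 - 18 = 19; latest 38 - 18 = 20 |
| Combined: D8, D18, then labs up to 3 days early | D8 to D18: 10 | 26 - 18 = 8 to 29 - 18 = 11 | 33 - 18 = 15 to 36 - 18 = 18; latest 37 - 18 = 19 |

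Under the text, nothing is scheduled after D8 until the cycle 2 labs (D9 to D28 if they are drawn on D29). Under the calendar, nothing is scheduled between the pre-study count and D18. The two gaps overlap on D9 to D17. Neither version schedules a count between D18 and the cycle 2 labs.

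**4. Result of combining.** With a D18 draw, the longest gap after the first ARQ 197 dose is 10 to 11 days nominally, or 15 to 18 (19 at the latest) if cycle 2 is a week late. For a draw on day d of week 3 (D15 to D21), the longest nominal gap is the larger of d - 8 and (cycle 2 lab day - d). It runs from 9 (d = 17, labs on D26: 9 and 9) to 14 (d = 15, labs on D29: 7 and 14).

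**The case against.** The strongest reply is that this is a typing error. Two narrative sections and most of the calendar's own footnotes point to D8. Blank cells in this grid are also weak evidence: the footnotes require the exam, blood pressure and EKG on C1D1, yet those rows are blank in week 1. On this view, changing footnote d and one cell to D8 cures the inconsistency, and a week 3 count goes beyond it. Lighter monitoring than in escalation may be deliberate.

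Most of this stands. A reader might infer that the two versions are equally likely to be the intended one; the evidence in the calendar does not support that. A reader might also take "To reduce the risk of severe myelosuppression events, a complete blood count (CBC) should be performed weekly during cycle 1" as the stated purpose of the expansion counts. That clause opens the sentence on the escalation phase, and the expansion schedule follows separately. Nor does the difference in cycle-start windows amount to a second defect. Footnote d allows "1 day for scheduling conflicts). For patients who have been on study for 6 or more cycles" and so on, but the opening of Section 10 already says "History and physical examination and laboratory evaluations can be performed up to 3 days before the start of the next cycle".

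What does not stand is that nothing needs doing. A coordinator who works from the calendar finds week 3 in the row and D18 in the footnote, and the two agree with each other. That coordinator has no scheduled reason to draw a CBC on D8. And if the text is simply restored, the only count that any current instruction places between D8 and the cycle 2 labs disappears.

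**Conclusion.** The contradiction is real and in current text. D1 and D8 is the more likely intention, but the calendar as written removes the D8 count before ARQ 197 and leaves no scheduled on-treatment count before D18, 17 to 20 days after baseline. If the text governs, the gap after D8 is 18 to 21 days nominally and 25 to 28 if cycle 2 is a week late. This concerns the 12 evaluable Cohort A patients and any replacements.

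The day counts assume that only scheduled draws occur. Clinically prompted counts remain allowed, and the biopsy follows Interventional Radiology procedures for platelets (Section 9.1.2.2), which may add a platelet count near D8. The documents do not say whether dosing continues during a week's delay.

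Three stronger readings are not supported. The MTD is not in doubt: escalation patients have weekly counts in cycle 1. No endpoint analysis is shown to change. And the number of Grade 3 or 4 events found late cannot be estimated, because the frequencies in Section 7.1 are not given by grade. Gaps should also be compared on equal terms: the late-start figure for the text (25 to 28 days) belongs beside the late-start figure for the combined schedule (15 to 18), not beside its nominal 10 to 11.

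**What to change.** Correct the Section 10.2 CBC row and footnote d to D1 and D8, and state that the D8 count comes before the first ARQ 197 dose. Keep the CBC already marked in week 3, drawn with the required week 3 liver tests on any day of that week. State the same schedule in Sections 5 and 5.3.3. Use up to 3 days before for cycle-start labs throughout, in place of the 1-day window in footnote d.

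Keeping the week 3 count goes a step beyond reconciling the text. If the sponsor prefers D1 and D8 alone, the protocol should say so in all three places, accepting the longer gap knowingly.

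The cost is wording in three places and at most one CBC tube per patient: at the week 3 liver draw if the text was intended, or at the D8 visit if the calendar was. Both are already planned, so no visit is added.

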5.1 Agent Administration

5.1.1 Dose Escalation Phase

A primary objective of the trial is to establish the safety, tolerability, and MTD of the combination. Pazopanib will be administered QD, starting at 400 mg, and ARQ 197 will be administered BID, starting at 120 mg (dose level 1). The duration of a cycle will be 28 days (\pm 1 day for scheduling). Dose escalation will proceed in cohorts of 3 patients each (3+3 design) as outlined below (Table 2):

Table 2: Dose Escalation Scheme

Dose Level	Pazopanib	ARQ 197
-2	200 mg QD	120 mg QD
-1	400 mg QD	120 mg QD
1 (starting dose)	400 mg QD	120 mg BID
2	600 mg QD	120 mg BID
3	600 mg QD	240 mg BID
4	800 mg QD	240 mg BID
5	800 mg QD	360 mg BID
6*	600 mg QD	360 mg BID

*If dose level 5 is above the MTD, dose level 6 will be evaluated.

Tumor biopsies will be optional during the escalation phase. For the escalation phase, 3 patients should have completed at least one cycle of therapy prior to considering dose escalation in the next cohort of patients. Dose escalation will proceed according to the following scheme. DLT is defined in [Section 5.2](#). Determination of DLT will be based on toxicities observed in the first cycle of therapy. Patients are considered evaluable for toxicity for the purpose of cohort dose escalation decisions if they either 1) experienced DLT or 2) have received at least 80% of the planned 28-day doses of treatment in one cycle of therapy and have been followed for one full cycle without DLT. All toxicities will be reported for all patients who receive any amount of study drug on this study. Evaluation of toxicity will begin with study drug administration on cycle 1 day 1.

Number of Patients with DLT at a Given Dose Level	Escalation Decision Rule
0 out of 3	Enter 3 patients at the next dose level.
≥ 2	Dose escalation will be stopped. This dose level will be declared the maximally administered dose (highest dose administered). Three (3) additional patients will be entered at the next lowest dose level if only 3 patients were treated previously at that dose.
1 out of 3	Enter at least 3 more patients at this dose level. 
 • If 0 of these 3 patients experience DLT, proceed to the next dose level. • If 1 or more of this group suffer DLT, then dose escalation is stopped, and this dose is declared the maximally administered dose. Three (3) additional patients will be entered at the next lowest dose level if only 3 patients were treated previously at that dose.
≤ 1 out of 6 at highest dose level below the maximally administered dose	This is generally the recommended Phase II dose. At least 6 patients must be entered at the recommended Phase II dose.

